2.2.6 Analysis of the Secondary Outcomes

The overall type I error for the secondary outcomes will be 0.05 (2-sided) without adjustment for multiple comparisons. We will apply the same analysis to the secondary outcome as the primary outcome.

2.2.6.1 Treatment Interactions by Co-Morbidity

The primary analysis of the treatment interaction with co-morbidity will take the form of a time to event, and will be analyzed using the same methodology (log-rank test) described for the primary outcome at a 0.05 2-sided significance level. The treatment effect will be summarized as a hazard ratio with 95% confidence interval. A test of treatment interaction by Charlson score <3 versus ≥ 3 (alternative subgroups) will also be performed.

In the study, the original Charlson score is a continuous variable. It is known that dichotomizing a continuous outcome into low or high values leads to a loss of information^{32,33}. Therefore, to keep the statistical power of the analysis, the testing of interaction will also be conducted by treating Charlson score as a continuous measure, via the Cox model, cf. the log-rank test for dichotomous formulation. The results from the above two methods will be compared, and they should be similar. In addition, a forest plot and treatment effects will be examined for each type of co-morbidity.

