The analysis of the primary outcome, all-cause mortality, will be analyzed as time to event and tested by the stratified log rank statistic (stratified on site and Charlson score <3 versus ≥ 3), with a type I error of 0.05 (2-sided). Cumulative survival rates will be calculated using the method of Kaplan-Meier. The treatment effect will be estimated from a stratified Cox proportional hazards model and summarized as a hazard ratio (ICD versus optimal medical therapy) with a 95% confidence interval. The assumption of proportionality will be tested by treatment by time

interaction term prior to fitting the model. The start time for all time-to-event analyses will be defined as the date of randomization and participants who do not experience an event will be right-censored at the date of last contact, date withdrawn, or date of study exit. VA Vital Status File will be used to determine the vital status of all study participants who are lost to follow-up at study exit.

3. Secondary Analyses

The overall type I error for the secondary outcomes will be of 0.05 (2-sided) without adjustment for multiple comparisons.

a) Treatment Interactions by Co-Morbidity

The primary analysis of the treatment interaction with co-morbidity will take the form of a time to event, and will be analyzed using the same methodology described for the primary outcome at a 0.05 2-sided significance level. A test of treatment interaction by Charlson score <3 versus ≥ 3 (alternative subgroups will also be explored) and by Charlson score as a continuous measure. In addition, a forest plot and treatment interaction will be examined for each type of comorbidity.

b) Quality of Life

The primary analysis of QoL will be a comparison between treatment groups of the change in the Minnesota Living with Heart Failure questionnaire scores at 12 months post-randomization relative to baseline using a two-sample t-test if the data appear sufficiently normal and a non-parametric method if the normality assumption looks like it does not hold.

4. Exploratory Analyses

a) Quality of Life

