2.2.3 Analysis of the Primary Outcome

For all the endpoints (primary, secondary, and exploratory) we will present summary information, as well as estimated result with p-value from an appropriately selected hypothesis test. The number of participants reaching the primary endpoint will be summarized in terms of total number participants as well as percent by treatment arm and treatment stratified by health stratum.

Treatment effect on the primary outcome, all-cause mortality, will be analyzed as time to event and tested by the stratified log rank statistic (stratified by Charlson score <3 versus ≥ 3), with a type I error of 0.05 (2-sided). Cumulative survival rates will be calculated using the method of Kaplan-Meier. The treatment effect will be estimated from a Cox proportional hazards model, adjusted by Charlson score and provided as a hazard ratio (ICD versus optimal standard of care) with a 95% confidence interval. The start time for all time-to-event analyses will be defined as the date of randomization and participants who do not experience an event will be right-censored at the date of last contact, date withdrawn, or date of study exit. VA Vital Status File will be used to determine the vital status of all study participants who are lost to follow-up at study exit.

Prior to Cox model fitting, the assumption of proportionality will be tested via treatment by time interaction term. If the assumptions of proportionality are not fulfilled, there will be no impact on the primary hypothesis test since we apply log-rank test on the primary

hypothesis test. We may estimate the hazard ratio by introducing interactions of treatment with function of time in the model. In addition, we will also test the treatment and Charlson stratum interaction in the Cox proportional hazards model²⁵. Breslow's approximation, which is the default in PROC PHREG in SAS, will be used to handle tied event times when ties are relatively few²⁶. If data are moderately- or heavily tied, we will use Efron's method, which gives closer results to the exact results than Breslow's approximation^{27,28}.

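### SAP 2.2.6.1 makes the log-rank test the primary analysis of the treatment-by-co-morbidity interaction, which that test cannot detect, and gives no valid interaction test primary status

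*Combined protocol and SAP*

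**What the plan says.** SAP 2.2.6.1 begins with what it labels the primary analysis of the interaction between treatment and co-morbidity, and states that it "will be analyzed using the same methodology (log-rank test) described for the primary outcome at a 0.05 2-sided significance level". The methodology referred to, in SAP 2.2.3, is a log-rank test stratified by Charlson score (<3 versus ≥3).

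The same section then lists two further tests:

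- "A test of treatment interaction by Charlson score <3 versus" 3 or more, introduced as an additional analysis and with no statistic named.
- A test of interaction "conducted by treating Charlson score as a continuous measure, via the Cox model, cf. the log-rank test for dichotomous formulation". The last clause gives the dichotomous form to the log-rank test for a second time. The next sentence says the two methods will be compared and predicts similar results.

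SAP 2.2.3, on the primary outcome, adds that "we will also test the treatment and Charlson stratum interaction in the Cox proportional hazards model".

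Protocol XV.C.3.a says the interaction "will be analyzed using the same methodology described for the primary outcome at a 0.05 2-sided significance level", and follows this with interaction tests on dichotomous and continuous Charlson. It does not name the log-rank test there. The primary methodology in protocol XV.C.2 covers a Cox model as well as the log-rank test: "The treatment effect will be estimated from a stratified Cox proportional hazards model".

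Protocol III.D ranks the effect by co-morbidity burden as a key secondary analysis. SAP 2.1 gives all secondary results an exploratory reading without multiplicity adjustment. Among the SAP's reporting shells, Table 24 holds one overall hazard ratio, and no table shows an interaction estimate or stratum-specific hazard ratios.

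**The concern.** A stratified log-rank test sums observed-minus-expected deaths over the strata and asks whether the sum differs from zero. It has power when the treatment effect points the same way in both Charlson groups, whether or not the effects are equal. When the effects point in opposite directions they cancel in the sum. It therefore answers the primary question a second time and says nothing about effect modification.

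The prediction of similar results carries the confusion into interpretation. A main-effect test and an interaction test address different hypotheses, so an analyst who follows the text has no valid rule for reading the pair. The SAP also does not say which of the several listed results decides the question. Protocol III.G.3 gives direct testing of this interaction as the reason for stratifying on co-morbidity rather than on age, so the deciding analysis should be unambiguous.

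**Working it through.** **Inputs.** From protocol XV.A: 1,462 participants, 565 deaths, 1:1 allocation, two-sided 0.05, 15% annual control mortality, hazard ratio (HR) 0.75, projected cumulative mortality 42.0% versus 34.1%, and equal enrollment in the two Charlson groups.

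**1. The plan's own figures.** The projected cumulative rates imply a crossover-diluted HR of ln(0.659)/ln(0.580) = 0.766. Schoenfeld power at 565 deaths is Φ(√565/2 × |ln 0.7656| − 1.96) = Φ(3.175 − 1.96) = 88.8%, close to the stated 90%. At the undiluted HR of 0.75 it is Φ(3.419 − 1.96) = 92.8%.

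Protocol XV.A.3 says significance will be reached if the effect is 50% larger in the low-burden group and 50% smaller in the high-burden group. Applied to the 25% hazard reduction, the HRs are 1 − 0.375 = 0.625 and 1 − 0.125 = 0.875, a ratio of 1.40. With 282.5 deaths per stratum, SE = √(4/282.5 + 4/282.5) = 0.168, z = ln 1.40/0.168 = 2.00 and p = 0.046. The statement therefore matches a Wald interaction contrast. Applied to the log hazard ratio instead, the ratio is 1.33, z = 1.71 and p = 0.087, which does not match.

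**2. The log-rank test used as an interaction test.** With equal strata, its z is about √E/2 times the mean of the two log hazard ratios.

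- HR 0.75 in both strata (no interaction): rejection is the main-effect power, 92.8%, or 88.8% after crossover dilution.
- HR 0.75 and 1.33 (strong interaction): the mean log hazard ratio is 0, so rejection is 5%.

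A simulation of 3,000 trials per scenario used N = 1,462, exponential survival at 15% annual control mortality, 102 patients followed for 5 years, the rest followed uniformly for 2 to 5 years, no crossover and equal strata. The comparator is the difference in stratum log hazard ratios divided by its standard error.

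| True HRs (Charlson <3; ≥3) | Stratified log-rank rejects | Interaction contrast rejects |
|---|---|---|
| 1; 1 | 5.2% | 4.8% |
| 0.75; 0.75 | 93.5% | 5.4% |
| 0.75; 1.33 | 6.2% | 95.2% |
| 0.625; 0.875 | 93.3% | 49.9% |

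**3. Should the two methods agree?** With no interaction and HR 0.75, treat the log-rank and interaction statistics as independent. Exactly one rejects with probability 0.928 × 0.95 + 0.072 × 0.05 = 0.885. With the diluted HR it is 0.888 × 0.95 + 0.112 × 0.05 = 0.849. Under the design assumptions the two results should usually disagree.

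**4. If the log-rank test were run separately in each stratum** (no section states this). With the same effect in both strata:

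- Equal split, 282.5 deaths each: power per stratum is 67.6% at HR 0.75, and exactly one stratum is significant in 2 × 0.676 × 0.324 = 44% of trials. At HR 0.766 the figures are 61.2% and 47%.
- Assumed 20/80 split of deaths (113 and 452): powers are 33.3% and 86.4% at HR 0.75, and exactly one is significant in 0.333 × 0.136 + 0.667 × 0.864 = 62%.

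The 20/80 split is an assumption. Protocol Table 7 puts 20.4% of systolic heart failure patients without an ICD, and 17.1% of those with one, below Charlson 3.

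**5. What a proper interaction test can detect.** With equal strata, power for a ratio of 1.40 is Φ(2.00 − 1.96) = 52%, and 80% power needs a ratio of exp(2.80 × 0.168) = 1.60. With 20% of deaths below Charlson 3, SE = √(4/113 + 4/452) = 0.210, power is 36% and the 80%-power ratio is 1.80.

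**The case against.** The strongest reply is that real interaction tests are planned. SAP 2.2.6.1 lists a dichotomous test and a continuous Cox test, SAP 2.2.3 pre-specifies the Cox interaction with Charlson stratum, and protocol XV.C.3.a lists both forms. The protocol's planning statement fits an interaction contrast, and secondary results are exploratory by the plan's own terms. All of this stands. It shows the right analysis will probably be run, and it limits the stakes. It does not settle which result is primary, because the SAP gives that label to the log-rank test and introduces the other tests as additions.

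Two stronger readings are tempting and are not supported:

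- A reader might infer that the question will be decided by comparing within-stratum p-values. No section describes running the log-rank test by stratum or comparing significance between strata. The figures in step 4 measure a risk if the text were taken that way; they are not the error rate of a planned analysis. The 62% also rests on a split that the protocol does not plan on: XV.A.3 assumes equal enrollment, and V.H expects a median Charlson score closer to 3 among eligible patients.
- A reader might infer that the protocol makes the same error. Its wording, "using the same methodology described for the primary outcome at a 0.05 2-sided significance level", takes in the Cox model, and an interaction test follows at once. Only the SAP adds the log-rank parenthesis.

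**Conclusion.** The point holds as a wrongly specified primary method for a key secondary question. In SAP 2.2.6.1 the named test rejects about 90% of the time when there is no interaction (88.8% to 93.5%, depending on whether crossover is allowed for) and about 5% to 6% when the effects are equal and opposite, so it carries no information about effect modification. The predicted agreement with the Cox test is also wrong.

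These sizes assume proportional hazards within strata, the planned number of deaths or a close approximation to it, and equal strata. The qualitative conclusion needs none of these assumptions, because it follows from what the statistic tests. The primary mortality analysis is unaffected. The SAP should be corrected, but the valid tests already listed and the exploratory status of secondary results keep this below a critical defect.

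**What to change.** In SAP 2.2.6.1:

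- Name the 1-df Wald or likelihood-ratio test of treatment × Charlson (<3 versus ≥3), in the Cox model already planned in SAP 2.2.3, as the primary interaction analysis. Choose one of the two statistics in advance.
- Report the ratio of hazard ratios with its 95% confidence interval, and the stratum-specific hazard ratios. Add space for these to the reporting tables.
- Keep the continuous-Charlson Cox interaction as supportive.
- Delete the parenthesis naming the log-rank test in the first sentence; in "via the Cox model, cf. the log-rank test for dichotomous formulation", delete everything after the comma; and delete the sentence predicting similar results from the two methods.

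The cost is SAP wording and one table shell. Sample size, the 565-death target and data collection do not change. The change does not raise power for the interaction, which stays at about 52% for the protocol's own scenario. Whether the models should also be stratified by site is a separate question that this point does not address.

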2.2.6.2 Quality of Life

The QoL will be measured by the Minnesota Living with Heart Failure questionnaire (MLHF), which contains 21 items that evaluate patients' perception of the effects of heart failure on their daily lives. In the questionnaire, each question is rated on a scale of 0 to 5, producing a total score between 0 and 105. The higher the score, the worse the quality of life. The total score will be treated as a continuous variable. The change in MLHF score at 12 months post-randomization relative to baseline will be calculated and tested for normality. If the distribution appears sufficiently normal, two sample t-test will be used to compare the difference between the two treatment groups. If not, a non-parametric method, such as the Wilcoxon rank-sum test will be used.

2.2.7 *Exploratory Analysis*

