	NYHA Class III	0.37 (0.15 – 0.90)
Bardy 2005 ²⁹	All patients	0.77 (0.62 – 0.96)
	Ischemic Chronic Heart Failure	0.79 (0.60 – 1.04)
	Non-Ischemic Chronic Heart Failure	0.73 (0.50 – 1.07)
	NYHA Class II	0.54 (0.40 – 0.74)
	NYHA Class III	1.16 (0.84 – 1.61)
Chan 2009 ⁵³	>75 years	0.59 (0.39 – 0.90)
Santangeli 2010 ⁶²	>60-65 years (meta-analysis)	0.75 (0.61 – 0.91)
Kong 2011 ⁷⁰	>75 years (meta-analysis)	0.73 (0.51 – 0.97)

The hazard ratio for effect of ICD therapy on all-cause mortality varies widely, primarily because of the differences in the populations analyzed in the various clinical trials. For this reason, it is a challenge to identify specific clinical trials on which to base our effect size assumption. However, two meta-analyses have been published that assess the impact of ICD on the elderly. In the assessment of the MADIT-II, DEFINITE, DINAMIT, SCD-HeFT and IRIS studies, a Hazard Ratio of 0.75 (95% CI 0.61 to 0.91) was found⁶²; and in a separate analysis of MADIT-I, MUSTT, MADIT-II, DEFINITE, and SCD-HeFT, a Hazard Ratio of 0.73 (95% CI

0.51 to 0.97) was found ⁷⁰. These Hazard Ratios are similar, and based on a sufficiently broad literature basis that they are the best point estimates of expectation for CSP #592. This study will adopt the more conservative of the two estimates, i.e. Hazard Ratio of 0.75.

2. Projected Sample Size

The following assumptions were used for the sample size calculation:

- Two-sided Type I error of 0.05
- Pilot stage with uniform recruitment over 1 year, with uniform follow-up of 5 years for all participants; 17 participants per site at 5 sites, i.e. $17 \times 5 = 85$ patient follow-up years
- Full-scale stage with uniform recruitment over 3 years (minimum follow-up = 2 years, maximum follow-up = 5 years, median follow-up = 3.5 years)
- Annual event rate of 15% in the control arm
- Hazard ratio of 0.75 (relative risk reduction = 23.5%)
- Allocation ratio of 1:1 for the treatment groups
- Annual drop in rate of 2.5% from the control group to the ICD group
- Drop-out rate of 1% from the ICD group to the control group in year 1 only.
- Annual loss-to-follow-up of 1%

Annual Event Rate in the Control Arm	Hazard Ratio		
	0.70	0.75	0.80
12%	1,177	1,771	2,881
15%	971	1,462	2,384
18%	834	1,258	2,057

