Because the VA Vital Status File will be searched for all deaths, loss-to-follow-up for the primary endpoint is considered to be very negligible and was therefore not accounted for in the sample size calculation. Based on a 15% annual event rate in the control arm and a hazard ratio of 0.75, and the other assumptions listed above, a sample size of 1,462 (565 total primary outcome events) will be needed in order to achieve 90% power with a 2-sided Type I error rate of 0.05.

Using the target sample size of 1,462, the following scenarios were considered as sensitivity analyses:

- If the recruitment rate is less than anticipated, the study will still maintain 80% power to detect a hazard ratio of 0.75 with 1,084 participants (422 events).
- If the control group annual event rate was 3% lower than anticipated (i.e. 12% annual mortality rate) the study would still maintain 81.0% power to detect a hazard ratio of 0.75.
- If the effect size is smaller than hypothesized, the study would still maintain 80% power to detect a hazard ratio of 0.78.

3. Power for Secondary Analyses

The secondary objectives for this trial are to test the treatment interactions by co-morbidity level, and to test the change from baseline in the Minnesota Living with Heart Failure score. Neither secondary analysis will require adjustment for type I error, i.e. no “multiple testing” corrections: adjustments for multiple comparisons are required in confirmatory whenever results from multiple tests have to be combined in one final conclusion and decision; in studies with a single primary endpoint, all other endpoints are considered subsidiary and their results can only have an exploratory rather than a confirmatory interpretation – multiplicity corrections are not required¹²⁴. A sample size of 1,462 participants will yield the following power for secondary endpoints:

- Assuming equal enrollment across high- and low-burden groups, this study will reach statistical significance for an increased in therapeutic effect by 50% in the low-burden group (Charlson <3) and decrease in efficacy of 50% in the high-burden group (Charlson ≥ 3). Assuming a pooled standard deviation of 5 for change from baseline in Minnesota Living with heart failure score, the study will have 80% power to detect a 0.73 difference between groups in mean change from baseline at 12 months.

B. Interim Monitoring and Analysis

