Early effects (QoL at 6 months), late effects (QoL at 24 months), and longitudinal effects (effect over 24 months) for the Minnesota Living with Heart Failure QoL data will also be assessed by a longitudinal repeated measures mixed effects analysis. All mixed models will be adjusted for the baseline Minnesota Living with Heart Failure score, and for the randomization design (site and co-morbidity burden). Site will be included in the model as a random effect and general health status (Charlson <3 versus ≥ 3) as a fixed effect. The outcome variable in the model will be the change in the Minnesota Living with Heart Failure Quality of Life Score at each follow-up contact relative to baseline. Model building methods will be used to first determine the best mean structure of the outcome (e.g., time as linear or categorical) and then to determine the best fitting and most parsimonious covariance structure for the data.

b) All-cause Hospitalization

Total hospitalizations, total number of days of hospitalization, and the proportion of participants who require at least one hospitalization during the follow-up period will be compared between treatment groups at a 0.05 significance level. No adjustment will be made for multiple testing for tertiary outcomes because they are considered exploratory in nature. The total hospitalizations and total days of hospitalization will be analyzed using generalized Poisson or negative binomial regression models. Proportion of participants requiring at least one hospitalization will be analyzed using a chi-square test statistic.

c) Sudden Cardiac Death

Time to event for sudden cardiac death will be analyzed using the same methodology described for the primary outcome at a 0.05 2-sided significance level. VA Vital Status File will be used to determine the vital status of all study participants who are lost to follow-up at study exit. VA Vital Status File search plus a NDI Plus database search for all participants who are found to have died through the VA database search in order to adjudicate the cause of death.

5. Analysis of Safety Data

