2.2.7.1 Quality of Life

The QoL score at each time point will be summarized in terms of mean and standard deviation by treatment arm and treatment by stratified health status.

Early effects (QoL at 6 months), late effects (QoL at 24 months), and longitudinal effects (effect over 24 months) for the Minnesota Living with Heart Failure QoL data will also be assessed by a longitudinal repeated measures mixed effects analysis.

The outcome variable in the mixed models will be the change in the MLHF QoL score at each follow-up visit relative to baseline, which is a continuous variable. Model building methods will be used to first determine the most parsimonious covariance structure for the data. The model will first be fit with an unstructured covariance matrix with time treated as a categorical variable. The mixed model will include the following covariate: baseline MLHF score (continuous variable), site as a random effect, and general health status (Charlson co-morbidity index) as a fixed effect and time, along with a time and treatment interaction term. A second model will be fit with an unstructured covariance matrix with time treated as a linear trend. The model will include treatment, time, and the treatment by linear time interaction plus the pre-determined covariates. A likelihood ratio test (LRT) will then be performed to determine if the linear trend (plus its interaction with treatment) is consistent with the data. If the simpler model with time as linear is sufficient, time will be treated continuously. If the fit is significantly improved with time as a categorical effect, then time will be included in the model as a categorical variable.

Once the mean structure of the model is determined, a LRT will be performed to determine whether a more parsimonious covariance structure e.g. autoregressive covariance structure 1 (AR1) or AR1 or compound symmetry (CS), will fit better. Once the mean and covariance structure are identified for this model, a treatment by time interaction will be examined. If the interaction term is not significant, it will be removed

from the model. If the treatment by time interaction is significant, then pairwise treatment comparisons will be performed at each time point separately.

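### The 80% power quoted for the 12-month MLHF comparison counts every randomised participant as measured; it is about 74% after the plan's own expected deaths, and the main test leaves out covariates already collected

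*Combined protocol and SAP*

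**What the plan says.** **Main analysis.** Protocol XV.C.3.b compares the arms on change in MLHF from baseline to 12 months, "using a two-sample t-test if the data appear sufficiently normal", and otherwise by a non-parametric method. SAP 2.2.6.2 says the same, that a "two sample t-test will be used to compare the difference between the two treatment groups", and names the rank-sum test as the fallback. Neither includes a covariate.

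**Power.** Protocol XV.A.3 introduces its secondary power figures with "A sample size of 1,462 participants will yield the following power for secondary endpoints". For MLHF it continues: "Assuming a pooled standard deviation of 5 for change from baseline", "the study will have 80% power to detect a 0.73 difference between groups in mean change from baseline at 12 months". It makes no allowance for deaths or missing questionnaires and gives no source for the SD.

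**Mortality.** Protocol XV.A.2 and SAP 2.1 assume "Annual event rate of 15% in the control arm", a hazard ratio of 0.75, 1% annual loss to follow-up and at least two years of follow-up.

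**Exploratory model.** Protocol XV.C.4.a says "All mixed models will be adjusted for the baseline Minnesota Living with Heart Failure score", and also for site and Charlson status. SAP 2.2.7.1 specifies the same covariates and then allows the model to be reduced: "If the simpler model with time as linear is sufficient, time will be treated continuously". A non-significant treatment-by-time term is dropped, and separate time-point comparisons follow only a significant one.

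**Other text.** SAP 2.2.6 says in general terms that secondary outcomes are analysed like the primary outcome. SAP 3.3 says QoL will be analysed with a longitudinal mixed model and plays missing data down.

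**The concern.** Two parts of one plan do not fit together. The sample-size section expects a substantial share of participants to die in the first year, yet the QoL power statement needs a month-12 score from everyone randomised. A participant who has died has no score, so the power of the stated test is lower than printed.

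Separately, the main test sets aside baseline information that is collected before randomisation and already written into another model for the same score. The exploratory model does not make up for this, because its reduction rules can leave no distinct adjusted contrast at month 12.

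At stake are the precision of a named secondary result and the accuracy of one printed figure. The trial's size is set by 565 deaths and is not affected.

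**Working it through.** **Inputs.** From Protocol XV.A.3: 731 per arm, SD of change 5, difference 0.73, power 80%. From Protocol XV.A.2 and SAP 2.1: control mortality 15% a year, hazard ratio 0.75, loss 1% a year, drop-in 2.5% a year, year-1 drop-out 1%. Two-sided alpha is 0.05. Minimum follow-up is two years, so nobody is administratively censored before month 12.

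**1. The plan's figure.** Detectable difference at 80% power = (1.960 + 0.842) × 5 × √(2/731) = 0.733. Power for 0.73 is 79.7%. The printed figure reproduces with all 1,462 measured.

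**2. Survivors at month 12.**
- OMT: 731 × 0.85 = 621.4, so 109.7 deaths.
- ICD: annual mortality = 1 − 0.85^0.75 = 11.5%, which matches the plan's stated 23.5% relative reduction. Survivors are 647.1, so 83.9 deaths.
- Total deaths: about 193.5 of 1,462 (13.2%).

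With the planned crossovers the survivors are 621.7 and 647.0, which changes nothing.

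**3. The stated test in survivors, SD 5.** Standard error = 5 × √(1/621.4 + 1/647.1) = 0.281. Detectable difference = 2.802 × 0.281 = 0.787. Power for 0.73 = Φ(0.73/0.281 − 1.960) = 73.9%. With the plan's 1% loss these become 0.791 and 73.4%.

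**4. Dependence on the SD.** The detectable difference scales with the SD. At assumed SDs of 7.5 and 10 it is 1.18 and 1.57 in survivors. At SD 10, power for 0.73 is about 29% with everyone measured and 25% in survivors.

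**5. What adjustment for baseline could gain.** Assume equal variance s² at baseline and month 12, with correlation ρ. The change score has variance 2s²(1 − ρ) and ANCOVA has residual variance s²(1 − ρ²). The ratio is (1 + ρ)/2, so the saving is (1 − ρ)/2 of the change-score variance. Holding the SD of change at 5 forces s = 5/√(2(1 − ρ)). The documents give neither ρ nor s, so every row below is an assumption.

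| ρ | Implied s | Variance saving | Power for 0.73, survivors |
|---|---|---|---|
| 0.4 | 4.6 | 30% | 87% |
| 0.7 | 6.5 | 15% | 80.5% |
| 0.875 | 10 | 6% | 77% |
| 0.944 | 15 | 3% | 75% |
| 0.969 | 20 | 1.6% | 75% |

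The saving is positive for any ρ below 1, but it may be large or trivial. The larger gains require a cross-sectional SD of 4.6 to 6.5 on a scale from 0 to 105.

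**The case against.** The strongest reply is that little depends on this. The detectable difference moves by 0.787 − 0.733 = 0.054 points on a 105-point scale. In the plan's own table of published MLHF effects, the smallest listed as significant is 4 points. For 4 points, survivors-only power is essentially 100% at SD 5 and 99.7% even at an assumed SD of 15. The plan also gives secondary results only an exploratory interpretation. This stands, and it limits the weight of the point. It does not make the printed 80% correct for 0.73.

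Second, a t-test on change is a legitimate test, an adjusted mixed model is already planned, and SAP 2.2.7.1 ends with pairwise comparisons of least-squares means at each time point. The first two parts stand: leaving out covariates does not bias the randomised comparison. The third helps only partly. Those comparisons belong to a graphical summary, and if the interaction has been dropped the model gives the same treatment difference at every visit, so no separate month-12 estimate remains.

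Third, SAP 2.2.6 and 3.3 can be read sensibly. The first is a general sentence, since nobody would run a log-rank test on a score. The second plausibly refers to the longitudinal model. A reader might infer a serious conflict over which analysis is the main one. The documents do not support that: Protocol XV.C.3.b and SAP 2.2.6.2 agree with each other and are specific. This is a wording matter.

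**Conclusion.** The point holds on the plan's own inputs. At SD 5, about 13% expected deaths reduce power for 0.73 points from 80% to about 74% and raise the difference detectable at 80% power to 0.79; adding 1% loss gives about 73% and 0.79. These results take the SD of 5 as given, and that unsourced value matters more than the deaths do.

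The main test is valid but less precise than one using baseline MLHF, Charlson stratum and site. A reader might infer that ANCOVA would restore 80% power, or detect 0.66 to 0.73 points. The documents do not support that. Those figures need ρ between 0.4 and 0.7, hence a cross-sectional SD of only 4.6 to 6.5. With an assumed cross-sectional SD of 10 to 20 the variance saving is 2% to 6% and power stays at 75% to 77%. The case for adjustment is that it costs almost nothing, not that its benefit is known.

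Nor does adjustment deal with death. About 110 and 84 deaths are expected by month 12, so either analysis compares survivors who have a score. ANCOVA does not remove selection by death.

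**What to change.** 1. In Protocol XV.A.3, restate the figure with expected survivors: 0.79 points at SD 5, or about 74% power for 0.73. Give the source of SD 5 or call it an assumption, and show a range, for example 1.18 at SD 7.5 and 1.57 at SD 10. Do not print a power or detectable difference for ANCOVA unless a sourced correlation supports it.

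2. In Protocol XV.C.3.b and SAP 2.2.6.2, make the main analysis an ANCOVA of 12-month MLHF on treatment, baseline MLHF, Charlson stratum and site (random). Alternatively, use the month-12 contrast of the planned mixed model, with time categorical and the treatment-by-time term always kept. Keep the t-test as supportive.

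3. Align the wording of SAP 2.2.6 and 3.3 with that choice.

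4. State that the 12-month comparison is among survivors with a score, and report deaths by arm alongside it.

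The cost is wording in the protocol and SAP. No new data are needed and the sample size does not change.
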